- a) Prior, current, or pending enrollment in a cognitive rehabilitation program or other specific TBI rehabilitation program; b) moderate to severe TBI or other major neurocognitive disorder; c) psychotic disorder (e.g., schizophrenia spectrum disorder, delusional disorder, schizotypal personality disorder, bipolar or depressive disorder with psychotic features); d) acute suicidal ideation; e) inpatient psychiatric hospitalization within the past 12 months; f) any other illness or condition that would preclude or predictably influence ability to appropriately engage in study visits, as determined by the study team; g) active receipt of other mental health services during enrollment or active intervention period, except for stable psychotropic medications (≥ 1 month with no dose or medication changes).

Given high documented rates of MH comorbidity among Veterans with history of mTBI, individuals with current depression or PTSD symptoms will be permitted to enroll, as long as symptoms are not so functionally-impairing that they would preclude study participation. Exclusion criteria **a-d** are similar to those reported in a previous trial of full-length PST (Bell et al., 2017). Criteria **e-f** were added to narrow the target sample to the most likely candidates for PC-MHI, as opposed to specialty MH treatment, programs. The purpose of criterion **g** is to improve the likelihood that observed treatment effects are due to participation in the

intervention as opposed to other mental health services. Relative to exclusion criterion **a**, participants who have previously completed a cognitive assessment for research or clinical purposes, or who have received general clinical feedback on cognitive performance will be permitted to enroll as these are considered routine care and not cognitive rehabilitation.

Phase 1 Measures and Materials.

Measures are described below and summarized in Table 1.

a) Study Pre-Screening: Will be conducted via EMR review to establish service era status, primary care enrollment, and age (inclusion criteria **a-c**), and chart data points that signal probable mTBI history (see below) or possible exclusion criteria.

b) Study Screening/ Baseline Assessment: Screening and baseline assessment will consist of the following measures that are estimated to require 15-30 minutes:

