Phase 1 Study Timeline

We expect that one to two participants will be enrolled per month over a 6-month period, which is reasonable given our experience of recruitment in other PC-MHI studies. Because we are gathering data from such a small sample (i.e., target of up to 12 participants) and will employ a rapid analytic approach, we do not anticipate significant delays.

Following completion of this study, our team will move to conduct a pilot RCT of this protocol in the next study phase. This will prepare us to submit a future application designed to test the intervention in a full-scale RCT.

Phase 2 Approach

General study flow is summarized by the following process and depicted in Figure 2:

1. Electronic medical record review will be used to identify potential candidates.
2. Recruitment letters and consent summaries will be sent to potential candidates, followed by a recruitment phone call. Up to 127 candidates will then be invited to attend a verbal consent session which will include administration of screening/baseline measures.
3. Eligible participants who provide consent to participate will then engage in the following major study activities completed through telehealth:
 - a. Receive either the test (E-PST) or control (Healthy Living Messages) per random assignment.
 - b. Complete a post-intervention assessment using standard measures/interviews as outlined below.
 - c. Complete a follow-up assessment using standard measures outlined below.
4. Participants will continue in usual primary care for any necessary medical management of symptoms. Treatment as usual is not a study condition. Should participants evidence elevated risk for suicidal or homicidal behavior during study procedures, they will be referred for any necessary crisis intervention, including referral to the VA Crisis Line.

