a) Pending, current, or prior 24-months enrollment in a cognitive rehabilitation program or other specific TBI rehabilitation program; b) moderate to severe TBI or other major neurocognitive disorder; c) psychotic disorder on problem list (e.g., schizophrenia spectrum disorder, delusional disorder, schizotypal personality disorder, bipolar or depressive disorder with psychotic features); d) acute suicidal ideation; e) inpatient psychiatric hospitalization within the past 12 months; f) any other illness or condition that would preclude or predictably influence ability to appropriately engage in study visits, as determined by the study team; g) active receipt of concurrent mental health services during active intervention period, except for stable psychotropic medications (≥ 1 month with no dose or medication changes).

Given high documented rates of MH comorbidity among Veterans with history of mTBI, individuals with current depression or PTSD symptoms will be permitted to enroll, as long as symptoms are not so functionally-impairing that they would preclude study participation. Exclusion criteria **a-d** are similar to those reported in a previous trial of full-length PST (Bell et al., 2017). Criteria **e-f** were added to narrow the target sample to the most likely candidates for PC-MHI, as opposed to specialty MH treatment, programs. The purpose of criterion **g** is to improve the likelihood that observed treatment effects are due to participation in the intervention as opposed to other mental health services. Relative to exclusion criterion **a**, participants who have previously completed a cognitive assessment for research or clinical purposes, or who have received general clinical feedback on cognitive performance will be permitted to enroll as these are considered routine care and not cognitive rehabilitation.

Phase 2 Measures and Materials.

Measures are described below and the proposed assessment schedule is summarized in Table 1. T1 and T3 assessments are estimated to require ≤70 minutes. As T2 assessments also include a brief qualitative interview, we estimate an approximate 90-minute time commitment for Veterans assigned to the E-PST arm.

a) Study Pre-Screening: Will be conducted via EMR review to establish service era status, primary care enrollment, and age (inclusion criteria **a-c**), and chart data points that signal probable mTBI history (see below) or possible exclusion criteria.

b) Study Measures:

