Phase 2 Procedures.

Chart Pre-Screening. Study staff will review VISN2 primary care clinic lists for Veterans who have mTBI-related diagnoses listed in their EMR data (e.g., problem lists, corresponding ICD-9 or ICD-10 diagnostic codes); meet the age, service-era, and primary care enrollment criteria; and whose EMRs do not include any obvious evidence of exclusion criteria listed above. Recruitment letters and informed consent summaries will then be sent to veterans who pass the pre-screening procedure.

Recruitment Phone Calls. Veterans who pass pre-screening procedures and who do not opt-out will be contacted by phone to discuss the study and gauge interest. Interested candidates will then be scheduled for a verbal consent appointment and baseline assessment.

Screening/ Baseline Assessment & Selection. The written informed consent summary will be reviewed with candidates. Candidates will have a copy of the consent summary in-hand as they review materials with staff. Veterans who provide verbal consent will be formally screened for eligibility using the T1 measures outlined above.

Randomization. Following completion of the T1 assessment, eligible participants will be randomized in equal proportions to the test (E-PST) or control using a stratified permuted block design. Block designs ensure treatment balance of participants by randomly assigning the same number of participants to each treatment condition within blocks (e.g. ABBA, ABAB, etc.). A stratified design ensures treatment balance across 1 or more prognostic factors. We plan to implement a stratified permuted block design using blocks of size 4 within low and high levels of the baseline psychological distress as measured by the BSI-18: 1) “mild to moderate” (BSI-18 GSI T-score 54-62); and 2) “severe” (BSI-18 GSI T-score ≥ 63). Our block design maintains treatment balance within levels of baseline psychological distress while ensuring that the overall imbalance is not too great. Since we expect that an overall small number of female participants will be enrolled in the RCT, the treatment groups might be imbalanced by gender (i.e., because randomization is more effective with larger n ’s). To account for this possible gender imbalance, we will also equalize the treatment groups according to gender, which will minimize the chance of gender confounding the treatment effect.

Table 2. Phase 2 Assessment Schedule

Measure	Chart Pre-Screen	T1	Mid- Intervention	T2	T3
Chart Pre-Screening Tool	•				

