- **Control intervention (Healthy Living Messages).** Healthy Living Messages includes up to six, 15 to 30-minute sessions of a supportive intervention that includes health coaching and symptom monitoring. Each of the healthy living messages included in this condition are evidence-based, already available for use in VA (Department of Veterans Affairs, 2017) and consistent with primary care goals. In order to deliver these messages as part of the attention control condition, 6 of 9 possible messages were selected for control sessions: 1-Be Involved in Your Health Care, 2-Get Recommended Screening Tests and Immunizations, 3-Be Physically Active, 4-Eat Wisely, 5-Strive for a Healthy Weight, and 6-Be Safe. One message (*Manage Stress*) was excluded because materials from VA's PST program are directly referenced; two others (*Limit Alcohol* and *Be Tobacco Free*) were excluded as they might not apply uniformly to participants. We anticipate that sessions will be scheduled approximately biweekly but will afford flexibility in scheduling to aid in our assessment of feasibility of this planned approach.

Patient Outcome Measurement. Post-intervention (T2) and follow-up assessments (T3) will be completed. At each study time point, participants will complete a series of common MH self-report measures and a standard battery of brief cognitive measures. Participants will be encouraged to complete each assessment regardless of whether they choose to continue attending intervention sessions or discontinue treatment at any point. At T2, E-PST participants will be asked to complete a brief qualitative interview to query their experiences with the intervention. Interviews will be recorded in order to allow for quality assurance efforts by study staff working under supervision of the PI.

Payment. Participants will be provided a maximum \$150 stipend for completing study assessments according to the following schedule: \$35 for T1; \$50 for T2; \$35 for T3; and a \$30 bonus to those who complete all assessments.

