Primary analyses will focus on detecting post-treatment change in psychological distress as measured by the BSI-18's GSI T-score. We will test the preliminary hypothesis that E-PST (vs. control) will be associated with reduced psychological distress as measured by BSI-18. BSI-18 data will be described with means, standard deviations and CIs at each time point and condition. To show central tendency, variation and potential trends over time, means and 95% CIs will be plotted across time for each condition. Additional line plots connecting means across time will overlay the CIs to help illustrate trends. To assist in developing a larger trial, an ES will be calculated at post treatment to describe the standardized difference between conditions. The ES will be calculated by dividing the difference in the mean BSI-18 score between conditions at post-treatment by the pooled standard deviation. Then, the upper limit of a one-sided 80% CI under the null hypothesis of no difference between groups (ES = 0) will be compared to the observed ES by using the non-central *t*-distribution method discussed by Cumming & Finch (2001). We opted for a one-sided CI because we are interested in progressing toward a larger trial based on some evidence of effectiveness. The lower end of the CI is not informative in this pilot as the progression towards a larger trial would not occur even if the control condition was marginally more effective than E-PST. While a standard 95% CI provides greater coverage of the population difference, it also requires a larger sample of patients and associated increases in cost and time. Therefore, we propose an 80% interval that provides reasonable assurance of making the correct decision to move on to a larger trial (Cocks & Torgerson, 2013) While primary analyses focus on psychological distress, post-treatment ES's will also be calculated for secondary outcomes, and a correlation matrix will be built to describe the degree of correspondence among all outcomes. Our goal is to calculate a preliminary ES estimate that is representative of the true population using the ITT principle. Thus, all patients who are complete a baseline assessment and are randomized will be included in our analysis. We plan to utilize two sophisticated methods with the first being Maximum Likelihood Estimation (MLE), and Multiple Imputation (MI) as the second. A multi-level model (MLM) will be developed using MLE to calculate means and standard errors that will be used in the formation of an ES. MLM provides unbiased parameter estimates under a missing at random (MAR) assumption without resorting to listwise deletion of patients due to missing data. While the validity of MAR cannot be fully determined from the data, the reason for the missingness may depend on observed co-variates. If the latter case is true, MI (see below) is a viable and powerful option for imputing

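### Does Phase 2 exclusion criterion g, worded by services received after randomisation, leave eligibility or the intention-to-treat comparison unsound?

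*Combined protocol and SAP*

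**What the plan says.** All places are in the combined protocol and SAP.

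- **Phase 2 Exclusion Criteria, g:** excludes for "active receipt of concurrent mental health services during active intervention period, except for stable psychotropic medications". The medication exception requires at least one month without a change. The purpose given for g is to "improve the likelihood that observed treatment effects are due to participation in the intervention as opposed to other mental health services".
- **Phase 1 Exclusion Criteria, g:** the counterpart reads "active receipt of other mental health services during enrollment or active intervention period", so it also named enrolment.
- **Phase 2 Procedures, Chart Pre-Screening:** only Veterans whose records show no obvious evidence of the listed exclusions go forward. The T1 session then screens formally for eligibility.
- **Phase 2 Procedures, Randomization:** "Following completion of the T1 assessment, eligible participants will be randomized in equal proportions to the test (E-PST) or control".
- **Phase 2 Approach, item 4:** "Participants will continue in usual primary care for any necessary medical management of symptoms". The same item provides for crisis referral.
- **Phase 2 Procedures, Patient Outcome Measurement:** "Participants will be encouraged to complete each assessment regardless of whether they choose to continue attending intervention sessions or discontinue treatment at any point".
- **Phase 2 Data Analysis, Quantitative Data Analysis:** "all patients who are complete a baseline assessment and are randomized will be included in our analysis".

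**The concern.** An exclusion criterion should be decidable at the moment of randomisation. Criterion g names only a period that lies after it. Its Phase 1 counterpart also covered enrolment, so the Phase 2 wording can look like a drafting loss.

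Three things could be at stake. If staff applied g during treatment and removed participants, that would conflict with the intention-to-treat rule. If a participant were referred in a crisis, or had a psychotropic drug changed in usual primary care, nothing says whether g is then met. And if later services go unrecorded, the pilot cannot show whether the purpose of g was achieved, or whether other care was used equally in the two arms.

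**Working it through.** **1. When eligibility is decided.** The order is chart pre-screen, recruitment call, consent and T1, randomisation, sessions. The exclusion list, g included, is checked at the chart pre-screen, and eligibility is settled at T1. No passage checks it again. The plan therefore does give a time for judging exclusions as a group, although it does not name g there and no T1 measure is described as recording service use. The one-month look-back in the medication exception also reads most naturally as a check made at entry. The workable reading is that staff ask, before randomisation, whether the Veteran is in other mental health care, or due to be, while the sessions run.

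**2. What happens after randomisation.** No passage withdraws a participant for starting other services. Follow-up is encouraged whether or not treatment continues, and the analysis set is everyone randomised with a baseline assessment. Together these rules cover the case.

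**3. What is recorded.** Table 2 has 23 rows. None is named as a service-use or medication record, and the chart tool is marked at pre-screen only. The feasibility metrics do not list such an item either, but they are introduced as examples and are scheduled at T1, mid-intervention, T2 and T3. The attached risk-management procedure is not in the document, so whether crisis referrals are logged there cannot be checked.

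**4. How often the case may arise.** The plan gives no rate. With 38 randomised and an assumed rate p, P(at least one) = 1 − (1 − p)^38 and the expected number is 38p.

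| Assumed p | P(at least one) | Expected number |
|---|---|---|
| 2% | 0.536 | 0.76 |
| 5% | 0.858 | 1.9 |
| 10% | 0.982 | 3.8 |

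This is the chance that the question comes up. It is not a bias.

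**5. Would precision suffer?** First, the plan's own figure. The upper limit of a one-sided 80% interval around zero is 2 × z(0.80)/√N. Setting it to 0.3 gives N = (2 × 0.8416/0.3)² = 31.48, rounded up to 32, as the Phase 2 Sample Size Justification states. With all 38 kept, the limit is 0.273. It is 0.298 at 32 and 0.302 at 31, so on this formula 38 − 32 = 6 participants could be lost for all reasons before the 0.3 target is missed. That margin would matter for g only if g were enforced by removing randomised participants, which the plan does not do.

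**6. Would the effect size shift?** If an extra fraction f of one arm started services worth b standard deviations (SD), the between-arm difference would move by f × b. Assumed values of f from 10% to 30% and b from 0.3 to 0.5 SD give 0.10 × 0.3 = 0.03 up to 0.30 × 0.5 = 0.15 SD. The direction depends on the arm. Rewording g at entry, or counting services afterwards, would not remove this shift. Under intention to treat it is part of what is estimated.

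**7. What a change would cost.** A service-use check at T2 and T3 means at most 38 × 2 = 76 checks. Judging g by services current at T1 would also alter eligibility: a Veteran whose services end between T1 and the first session is not excluded by the present wording but would be under that rule. The plan already expects to solicit up to 127 people to randomise 38 (0.30 × 127 = 38.1).

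**The case for a change.** The best case for a change is that the gap is real and cheap to close. Other Phase 2 criteria carry explicit time anchors: TBI rehabilitation covers pending, current or the prior 24 months, and psychiatric admission the past 12 months. Criterion g has no such anchor. Participants are distressed by design, since a BSI-18 T-score above 53 is required, so changes of care during follow-up are foreseeable. The plan says that missed sessions and assessments are not protocol deviations but is silent on g. The qualitative interview is for the E-PST arm only, so anything it picks up about other care cannot be compared between arms. Counts of outside services by arm would help to design the multisite trial, which is a stated aim.

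Most of this stands as description. The wording of g could be tidier, and no visible item is named as capturing later services. What does not stand is the step to a defect. Dropping enrolment from g may have been deliberate, since criterion a was also reworded between the phases, from any prior programme to the last 24 months. The text on usual primary care and crisis referral does not contradict g, because neither passage says that such care makes a randomised participant ineligible. Whether such care should count under g is a clinical matter and is not judged here.

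**Conclusion.** No change is needed. This is missing detail that staff and analysts can fill sensibly from the rest of the plan: judge eligibility before randomisation, keep following everyone, and analyse everyone randomised. No bias is shown, the sample sizes of 32 and 38 are untouched, and the intention-to-treat comparison stays sound.

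The conclusion rests on two assumptions: that g is not enforced by removing randomised participants, which no passage proposes, and that the analysis-set rule is followed as written. The rates of 2% to 10% and the shifts of 0.03 to 0.15 SD are illustrations from assumed inputs, not estimates for this trial. The sponsor may still choose to state a reference time for g, to say how it sits with usual primary care and crisis referral, and to report later mental health services by arm. Those steps would help the next trial and would not alter a result of this one.

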- Qualitative Interview: A brief semi-structured interview designed to gather patient feedback on EPST at the conclusion of treatment. E-PST participants will be asked to provide details on their satisfaction with the treatment experience, acceptability of treatment components, perceived benefits of treatment, and reasons for treatment completion and/ or dropout. A tentative interview schedule is included as an attachment.

c) Feasibility data will be internally monitored. Because feasibility is a study aim, missing items/ assessments and alterations in scheduling will not be reported as protocol deviations, but will be treated as specific study data points. Examples of evaluation metrics include:

- *Feasibility of recruitment statistics*: the relative proportion of Veterans excluded per pre-screening criteria vs. screen-eligible Veterans; the relative proportion of screen pass vs. screen failures; reasons for screen failures; the number of participants enrolled per week; total time to sample accrual; and the proportion of the intent-to-treat sample with clinically-significant depression, and/or PTSD.

- *Feasibility of retention statistics*: the number of sessions attended per participant; mean and range of number of sessions attended overall; the relative proportion of participants who complete all six possible sessions vs. drop out of treatment; and reasons for treatment completion and dropout (as measured by qualitative interview described above).
- *Feasibility of measurement statistics*: completion rates, time estimates for each study measure and homework assignment, and recording participant questions, comments (e.g., requests for clarification, level of burden, items left blank).
- *Patient-level treatment fidelity statistics*: Veteran rates of completion of at-home assignments (e.g., Veterans are asked to practice specific E-PST and compensatory skills, record practice).
- *Therapist-level feasibility and fidelity indicator statistics*: training required for study therapist(s) (i.e., time, intensity); session length; therapist protocol adherence (i.e., proportion of essential actions completed on a fidelity checklist); remedial actions required (i.e., frequency, type); and time required to complete review of session tapes and rating forms. Rating forms will be revised to use for therapist training and supervision purposes, with content coinciding with the E-PST intervention manual (e.g., session content, coverage, frequency, and duration).

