Demographic Survey		•			
Ohio State Traumatic Brain Injury Identification Method-Short Form (OSU TBI-ID)		•			
Neurobehavioral Symptom Inventory (NSI)		•		•	•
Brief Symptom Inventory-18 (BSI-18)		•		•	•
Patient Health Questionnaire-9 (PHQ-9)		•		•	•
PTSD Checklist for DSM-5 (PCL5)		•		•	•
Coronavirus Anxiety Scale (CAS)		•		•	•
Applied Cognition-General Concerns-Short Form (ACGC-8a)		•		•	•
Applied Cognition-Abilities-Short Form (ACA-8a)		•		•	•
Hopkins Verbal Learning Test-Revised (HVLT-R)		•		•	•
Trail Making Test Parts A and B (TMT-A, TMT-B)		•		•	•
Wechsler Adult Intelligence Scale- Fourth Edition (WAIS-IV) Digit Span		•		•	•
Alcohol Use Disorders Identification Test (AUDIT)		•		•	•
Brief Addictions Monitor-Revised (BAM-R)		•		•	•
Pain Symptom Survey (PEG)		•		•	•
World Health Organization Quality of Life - BREF (WHOQOL-BREF)		•		•	•
General Self-Efficacy Scale (GSES)		•		•	•
Patient Global Impressions of Change (PGIC)				•	•
Client Satisfaction Questionnaire (CSQ)				•	•
Qualitative Interview				•	
Behavioral Health Measure-20 (BHM-20) Life Functioning Subscale			•		
Feasibility Metrics		•	•	•	•

Intervention. The test (E-PST) or control intervention will be administered to participants by a trained, therapist (Master's level-equivalent or higher). Psychological distress data (BHM-20 life-functioning subscale) will be collected during treatment sessions as part of routine outcome monitoring. Sessions will be audio-recorded for training and supervision purposes.

- **Test intervention (E-PST).** E-PST consists of 6, approximately 30-minute sessions focused on: a) reducing psychological distress by enhancing specific problem-solving skills; and b) developing specific cognitive and behavioral skills that target common cognitive inefficiencies reported in Veterans with mTBI history. The current therapist guide and participant workbook are included with this submission. We anticipate that sessions will be scheduled approximately biweekly but will afford flexibility in scheduling to aid in our assessment of feasibility of this planned approach.

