Risk Management. RA's will monitor for signals of clinical need at study assessment time points (e.g., participant statements of concern, ratings of suicidal ideation), and study therapist(s) will monitor such signals at intervention visits. New or worsening ratings that pertain to suicidal ideation will be addressed using the attached risk management procedure. This procedure has been successfully implemented in several prior studies. Adverse events will be monitored and reported according to institutional protocols.

Phase 2 Data Analysis

As noted above, this study is designed to achieve 3 goals: a) estimate a preliminary ES for our primary outcome measure (i.e., psychological distress as measured by the BSI-18); b) determine the feasibility of the assessment plan; and c) establish the feasibility of recruitment and retention in order to plan for a future multisite efficacy trial. We will employ a sequential explanatory mixed-methods approach (i.e., quantitative data collection, followed by qualitative data collection) to address these research questions.

a) Quantitative Data Analysis:

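### Phase 2 names one source for dropout reasons, an interview given only to the E-PST arm at T2, so no source is specified for controls or for E-PST participants who miss T2

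*Combined protocol and SAP*

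**What the plan says.** All references are to the Phase 2 part of the combined protocol and SAP.

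- **Goal.** Phase 2 Data Analysis gives the third aim of the pilot as to "establish the feasibility of recruitment and retention in order to plan for a future multisite efficacy trial". It is not limited to one arm.
- **Metric and its source.** In Phase 2 Measures and Materials, under the feasibility of retention statistics, one item is "reasons for treatment completion and dropout (as measured by qualitative interview described above". No second instrument is named. The item beside it is "the relative proportion of participants who complete all six possible sessions vs. drop out of treatment", which is stated for participants in general.
- **Who is interviewed.** The description of the interview in the same section says "E-PST participants will be asked to provide details on their satisfaction with the treatment experience, acceptability of treatment components" and goes on to include reasons for finishing or leaving treatment. It mentions no control participants.
- **When.** Phase 2 Procedures, Patient Outcome Measurement: "At T2, E-PST participants will be asked to complete a brief qualitative interview to query their experiences with the intervention". In Table 2 the row "Qualitative Interview" carries one mark, under T2.
- **Burden.** The introduction to the measures adds the interview to the T2 time for one arm only: "we estimate an approximate 90-minute time commitment for Veterans assigned to the E-PST arm".
- **Assessment after stopping.** Patient Outcome Measurement also says: "Participants will be encouraged to complete each assessment regardless of whether they choose to continue attending intervention sessions or discontinue treatment at any point".

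**The concern.** Both arms are offered up to six sessions, and people can stop in either. A multisite trial planned from this pilot would need to know why they stop in each arm. The plan counts sessions and completers in both arms, but it ties the reasons to an instrument that half of the randomized participants never receive. In the E-PST arm, that instrument also misses anyone who does not come back for T2, and a retention plan most needs to understand that group.

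The wording probably came over from Phase 1, which lists the same metric with the same source. Phase 1 had a single arm and an interview after every session, so reasons could surface as they arose. Phase 2 added a control arm and cut the interview to one occasion in one arm, and the source of the metric was not changed to match. That history is an inference, and the point does not depend on it.

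At stake is one component of a stated feasibility goal.

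**Working it through.** The plan gives no figure for this metric, so there is none to reproduce. The check is a cross-reading followed by a head count.

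**Step 1: which participants have a named source for their reasons?**

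| Group | Interview offered? | Other named source of reasons |
|---|---|---|
| E-PST, attends T2, finished sessions | Yes | not needed |
| E-PST, attends T2, stopped sessions early | Yes; T2 is sought after stopping | not needed |
| E-PST, misses T2 | No; the interview is not repeated at T3 | none |
| Control, any status | No | none |

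The metric, the interview description, the T2 time estimate, Table 2 and the outcome procedures all agree on this, so it is not a slip in one sentence.

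**Step 2: does another provision fill the gap?**

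- Phase 2 Participants, Recruitment, and Enrollment allows as-needed contact with participants, including outreach, but does not ask for or record a reason for stopping.
- Phase 2 Data Attrition commits to collecting and analyzing dropout data, but names no reasons, instrument or arm.
- Table 2 marks feasibility metrics at T1, mid-intervention, T2 and T3 without separating the arms, but for this metric the named source is the interview.

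None of the three specifies a field for the reason.

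**Step 3: how many participants could the interview reach?**

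Inputs:
- 38 randomized, 19 per arm (Phase 2 Participants, Recruitment, and Enrollment).
- 6% attrition over 12 weeks and 20% over 6 months, the latter adopted as the upper limit of data attrition (Phase 2 Data Attrition).
- Assumptions: T2 loss lies between these two rates and is equal in the two arms, and everyone who attends T2 in the E-PST arm agrees to the interview.

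Formula: maximum reached = 19 × (1 − d), where d is the proportion lost at T2; share of all randomized = 19 × (1 − d) / 38.

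- d = 0: 19 of 38 = 50%. The control arm alone removes half.
- d = 0.06: 19 × 0.94 = 17.86, about 18 of 38; 17.86 / 38 = 47%.
- d = 0.20: 19 × 0.80 = 15.2, about 15 of 38; 15.2 / 38 = 40%.

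These are counts of participants who could be asked why they finished or left. They are not counts of people expected to leave.

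**The case against.** **The gap is one of specification only.** The metrics are introduced as examples, feasibility data are to be monitored internally, contact with participants is allowed as needed, and dropout data are promised. The interview schedule is an attachment that is not in the documents. A reader might infer that control-arm reasons cannot be obtained at all. The documents do not support that: staff could ask, and nothing forbids it. What stands is that no source is specified. The list being illustrative does not remove this, because this item is on it with its instrument named.

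**Leaving treatment is not the same as missing T2.** The metric is about treatment dropout, and T2 is sought from people who have stopped sessions. E-PST participants who stop but attend T2 are therefore covered. This stands and narrows the gap to controls and to E-PST participants absent at T2.

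**The 20% is not a treatment-dropout rate.** A reader might multiply 19 by 20% and call the result the number of dropouts in each arm. The plan adopts 20% as a ceiling on data attrition, from a 6-month reference, and gives no rate for stopping treatment. The figure serves only to bracket attendance at T2. If T2 falls about 12 weeks after the start (six roughly biweekly sessions; an assumption), the 6% figure is the closer guide.

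**The primary analysis does not need these reasons.** A reader might infer that the missing-at-random assumption or the imputation model is undermined. It is not. The imputation guideline in Phase 2 Plan to Address Missing Data uses measured variables, and a reason recorded only for those who stop is undefined for everyone else, so it is not an ordinary imputation predictor.

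**Restricting the interview to E-PST looks deliberate.** It collects views on the treatment being developed, and that is sensible. It does not explain why a trial-wide retention statistic should rest on it alone.

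**Conclusion.** The point holds in a limited form. As written, the plan specifies no source of dropout reasons for the 19 control participants or for E-PST participants who miss T2, while the goal and the companion retention statistics cover the whole trial. On the stated assumptions (T2 loss of 6% to 20%, equal across arms, and full consent to the interview), the named source reaches at most about 15 to 18 of 38 participants. The first part rests on the text alone; only the range depends on the assumed loss.

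The consequence is confined to one descriptive component of retention feasibility. Sessions attended and the proportion completing remain available in both arms, and the effect size, its confidence limit and the sample size do not change. With so few participants, recorded reasons would describe why people left but could not establish a difference between arms. This is a cheap improvement to make before the data are collected, and it does not invalidate the design.

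**What to change.** In Phase 2 Measures and Materials, under the feasibility of retention statistics:

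1. Add one reason-for-discontinuation item, recorded by staff in both arms at the existing follow-up contact when a participant stops or misses sessions. Include unable to contact as a permitted code, so that silence is counted and not left blank.
2. Ask the same item once at T2 in both arms.
3. Name this item, together with the interview, as the source of the reasons metric.
4. Leave the E-PST interview unchanged, including its question on reasons for completion and dropout. A discontinuation item cannot capture why people finish, so removing that question would lose half of the metric.

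The cost is one item on the contact record, about a minute of staff time per dropout, and one extra item at T2. No visit, staff member or participant is added. Some lost participants will still give no reason, but their number in each arm will be known.
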